### **10.2 Procedures for AE and SAE Recording and Reporting**

Participating investigators will assess the occurrence of AEs and SAEs at all participant evaluation time points during the study.

All AEs and SAEs whether reported by the participant, discovered during questioning, directly observed, or detected by physical examination, laboratory test or other means, will be recorded in the participant's medical record and on the appropriate study-specific case report forms.

The descriptions and grading scales found in the revised NCI Common Terminology Criteria for Adverse Events (CTCAE) version 4.0 will be utilized for AE reporting. All appropriate treatment areas should have access to a copy of the CTCAE version 4.0.

A copy of the CTCAE version 4.0 can be downloaded from the CTEP website at:

[http://ctep.cancer.gov/protocolDevelopment/electronic\\_applications/ctc.htm](http://ctep.cancer.gov/protocolDevelopment/electronic_applications/ctc.htm).

### **10.3 Reporting Requirements**

For multi-site trials where a DF/HCC investigator is serving as the principal investigator, each participating investigator is required to abide by the reporting requirements set by the DF/HCC. The study must be conducted in compliance with FDA regulations, local safety reporting requirements, and reporting requirements of the principal investigator.

Each investigative site will be responsible to report SAEs that occur at that institution to their respective IRB. It is the responsibility of each participating investigator to report serious adverse events to the study sponsor and/or others as described below.

CONFIDENTIAL

This document is confidential. Do not disclose or use except as authorized.

## **10.4 Reporting to the Study Sponsor 10.4.1**

### **Serious Adverse Event Reporting**

All serious adverse events that occur after the initial dose of study treatment, during treatment, or within 30 days of the last dose of treatment must be reported to the DF/HCC Overall Principal Investigator on the local institutional SAE form. This includes events meeting the criteria outlined in Section 10.1.2, as well as the following:

- Grade 2 (moderate) and Grade 3 (severe) Events – Only events that are unexpected and possibly, probably or definitely related/associated with the intervention.
- All Grade 4 (life-threatening or disabling) Events – Unless expected AND specifically listed in the protocol as not requiring reporting.
- All Grade 5 (fatal) Events – When the participant is enrolled and actively participating in the trial OR when the event occurs within 30 days of the last study intervention.

Note: If the participant is in long term follow up, report the death at the time of continuing review.

Participating investigators must report each serious adverse event to the DF/HCC Overall Principal Investigator as well as the Astellas Safety Department within 24 hours of learning of the occurrence. In the event that the participating investigator does not become aware of the serious adverse event immediately (e.g., participant sought treatment elsewhere), the participating investigator is to report the event within 24 hours after learning of it and document the time of his or her first awareness of the adverse event. Report serious adverse events by telephone, email or facsimile both to:

DF/HCC Overall Principal Investigator and Medical Monitor:

[name]  
[[contact]](mailto:[contact])  
[contact]  
[contact]

Astellas Safety Department:

Astellas Pharma Global Development – United States  
Email: [[contact]](mailto:[contact])  
[contact]

Within the following 24-48 hours, the participating investigator must provide follow-up information on the serious adverse event. Follow-up information should describe whether the event has resolved or continues, if and how the event was treated, and whether the participant will continue or discontinue study participation.

#### **10.4.2 Non-Serious Adverse Event Reporting**

Non-serious adverse events will be reported to the DF/HCC Overall Principal Investigator on the toxicity Case Report Forms.

#### **10.5 Reporting to the Institutional Review Board (IRB)**

Investigative sites within DF/HCC will report all serious adverse events directly to the DFCI Office for Human Research Studies (OHRS).

Other investigative sites should report serious adverse events to their respective IRB according to the local IRB's policies and procedures in reporting adverse events. A copy of the submitted institutional SAE form should be forwarded to:

Office for Human Research Studies  
Dana Farber Cancer Institute  
[name] (physical location)  
[name] (mailing  
location)

[name]

[contact]

[contact]

The DF/HCC Principal Investigator will submit SAE reports from outside institutions to the DFCI Office for Human Research Studies according to DFCI IRB policies and procedures in reporting adverse events.

#### **10.6 Reporting to the Food and Drug Administration (FDA)**

Use on Med watch form 3500A

#### **10.7 Reporting to Hospital Risk Management**

Participating investigators will report to their local Risk Management office any subject safety reports or sentinel events that require reporting according to institutional policy.

#### **10.8 Monitoring of Adverse Events and Period of Observation**

All adverse events, both serious and non-serious, and deaths that are encountered from initiation of study intervention, throughout the study, and within 30 days of the last study intervention should be followed to their resolution, or until the participating investigator assesses them as stable, or the participating investigator determines the event to be irreversible, or the participant is lost to follow-up. The presence

Version 13.0 Protocol Version Date: 1/09/2015  
and resolution of AEs and SAEs (with dates) should be documented on the appropriate case report form and recorded in the participant's medical record to facilitate source data verification.

For some SAEs, the study sponsor or designee may follow-up by telephone, fax, and/or monitoring visit to obtain additional case details deemed necessary to appropriately evaluate the SAE report (e.g., hospital discharge summary, consultant report, or autopsy report).

Participants should be instructed to report any serious post-study event(s) that might reasonably be related to participation in this study. Participating investigators should notify the DF/HCC Overall Principal Investigator of greater or equal to grade 3 events and the IRB of any unanticipated death or adverse event occurring after a participant has discontinued or terminated study participation that may reasonably be related to the study.

## 11. DATA AND SAFETY MONITORING

### 11.1 Data Reporting

#### 11.1.1 Method

The QACT will collect, manage, and monitor data for this study.

#### 11.1.2 Data Submission

The schedule for completion and submission of case report forms (paper or electronic) to the QACT is as follows:

Form	Submission Timeline
Eligibility Checklist	Complete prior to registration with QACT
On Study Form	Within 14 days of registration
Baseline Assessment Form	Within 14 days of registration
Treatment Form	Within 10 days of the last day of the cycle
Adverse Event Report Form	Within 10 days of the last day of the cycle
Response Assessment Form	Within 10 days of the completion of the cycle required for response evaluation
Off Treatment/Off Study Form	Within 14 days of completing treatment or being taken off study for any reason

Follow up/Survival Form	Within 14 days of the protocol defined follow up visit date or call
-------------------------	---

## 11.2 Safety Meetings

The DF/HCC Data and Safety Monitoring Committee (DSMC) will review and monitor toxicity and accrual data from this trial. The committee is composed of clinical specialists with experience in oncology and who have no direct relationship with the study. Information that raises any questions about participant safety will be addressed with the Principal Investigator and study team.

The DSMC will meet quarterly and/or more often if required to review toxicity and accrual data. Information to be provided to the committee may include: up-to-date participant accrual; current dose level information; DLT information; all grade 2 or higher unexpected adverse events that have been reported; summary of all deaths occurring within 30 days; any response information; audit results, and a summary provided by the study team. Other information (e.g. scans, laboratory values) will be provided upon request.

## 11.3 Ongoing Monitoring of Protocol Compliance

At the Discretion of the Overall Investigator, the Participating Institutions will be required to submit participant source documents to the DF/HCC Lead Institution for remote monitoring by the Clinical Trial Specialist and or Lead site coordinator.

At the Discretion of the Overall Investigator, the Participating Institution may require at least one on-site monitoring visit conducted by the Overall Investigator and or Clinical Trial Specialist and or Lead site Coordinator. The DF/HCC Lead Institution will implement monitoring activities ongoing to ensure that Participating Institutions are complying with regulatory and protocol requirements, data quality, and participant safety. Additional monitoring practices may include but are not limited to: source verification, review and analysis of the following: eligibility requirements of all participants , informed consent procedures, adverse events and all associated documentation, study drug administration / treatment, regulatory records and site trial master files, protocol deviations, pharmacy records, response assessments, and data management.

Monitoring can occur during any time during a site's participation up unto and including study completion.

All data submitted to the DF/HCC QACT will be monitored for timeliness of submission, completeness, and adherence to protocol requirements. The Lead Institution or designee and if applicable QACT Data Analysts assigned to the Protocol will perform the ongoing protocol data compliance monitoring with the support of the Participating Institution's Principal Investigator and research team. The DF/HCC Lead Institution will maintain regular and ongoing communication to Participating Institutions about study related information.

## 12. REGULATORY CONSIDERATIONS

### 12.1 Protocol Review and Amendments

This protocol, the proposed informed consent and all forms of participant information related to the study (e.g., advertisements used to recruit participants) and any other necessary documents must be submitted, reviewed and approved by a properly constituted IRB governing each study location.

Any changes made to the protocol must be submitted as amendments and must be approved by the IRB prior to implementation. Any changes in study conduct must be reported to the IRB. The DF/HCC Overall Principal Investigator (or Protocol Chair) will disseminate protocol amendment information to all participating investigators.

All decisions of the IRB concerning the conduct of the study must be made in writing.

### 12.2 Informed Consent

All participants must be provided a consent form describing this study and providing sufficient information for participants to make an informed decision about their participation in this study. The formal consent of a participant, using the IRB approved consent form, must be obtained before the participant is involved in any study-related procedure. The consent form must be signed and dated by the participant or the participant's legally authorized representative, and by the person obtaining the consent. The participant must be given a copy of the signed and dated consent document. The original signed copy of the consent document must be retained in the medical record or research file.

### 12.3 Ethics and Good Clinical Practice (GCP)

This study is to be conducted according to the following considerations, which represent good and sound research practice:

- E6 Good Clinical Practice: Consolidated Guidance  
[www.fda.gov/downloads/RegulatoryInformation/Guidances/UCM129515.pdf](http://www.fda.gov/downloads/RegulatoryInformation/Guidances/UCM129515.pdf)
- US Code of Federal Regulations (CFR) governing clinical study conduct and ethical principles that have their origin in the Declaration of Helsinki
  - Title 21 Part 11 – Electronic Records; Electronic Signatures  
[www.access.gpo.gov/nara/cfr/waisidx\\_02/21cfr11\\_02.html](http://www.access.gpo.gov/nara/cfr/waisidx_02/21cfr11_02.html)
  - Title 21 Part 50 – Protection of Human Subjects  
[www.access.gpo.gov/nara/cfr/waisidx\\_02/21cfr50\\_02.html](http://www.access.gpo.gov/nara/cfr/waisidx_02/21cfr50_02.html)
  - Title 21 Part 54 – Financial Disclosure by Clinical Investigators  
[www.access.gpo.gov/nara/cfr/waisidx\\_02/21cfr54\\_02.html](http://www.access.gpo.gov/nara/cfr/waisidx_02/21cfr54_02.html)
  - Title 21 Part 56 – Institutional Review Boards  
[www.access.gpo.gov/nara/cfr/waisidx\\_02/21cfr56\\_02.html](http://www.access.gpo.gov/nara/cfr/waisidx_02/21cfr56_02.html)

Version 13.0 Protocol Version Date: 1/09/2015

- Title 21 Part 312 – Investigational New Drug Application  
[www.access.gpo.gov/nara/cfr/waisidx\\_02/21cfr312\\_02.html](http://www.access.gpo.gov/nara/cfr/waisidx_02/21cfr312_02.html)

- State laws
- DF/HCC research policies and procedures <http://www.dfhcc.harvard.edu/clinical-researchsupport/clinical-research-unit-cru/policies-and-procedures/>

It is understood that deviations from the protocol should be avoided, except when necessary to eliminate an immediate hazard to a research participant. In such case, the deviation must be reported to the IRB according to the local reporting policy.

## **12.4 Study Documentation**

The investigator must prepare and maintain adequate and accurate case histories designed to record all observations and other data pertinent to the study for each research participant. This information enables the study to be fully documented and the study data to be subsequently verified.

Original source documents supporting entries in the case report forms include but are not limited to hospital records, clinical charts, laboratory and pharmacy records, recorded data from automated instruments, microfiches, photographic negatives, microfilm or magnetic media, and/or x-rays.

## **12.5 Records Retention**

All study-related documents must be retained for the maximum period required by applicable federal regulations and guidelines or institutional policies.

# **13. STATISTICAL CONSIDERATIONS**

## **13.1 Sample Size/Accrual Rate**

The primary objective is to estimate the proportion of patients having intermediate risk CaP treated with external beam radiation therapy (EBRT) and enzalutamide whose PSA level at the end of six cycles of enzalutamide and EBRT is  $\leq 0.2$  ng/ml. In a single stage design, seventy-one patients will be enrolled. Assuming 10% ineligibility, the target evaluable sample size is 64 patients. The null hypothesis is 60% of patients achieving PSA nadir  $\leq 0.2$  ng/ml. The historical rate will serve as the alternative in this design. Based on research by D'Amico et al, the proportion of patients achieving PSA level  $\leq 0.20$  ng/ml at the end of EBRT and 6 months of leuprolide acetate neo-adjuvant/adjuvant treatment is 75%. With a sample size of 64 evaluable patients, if the number achieving PSA level  $\leq 0.2$  ng/ml is 44 or more, then the hypothesis that the percentage achieving PSA level  $\leq 0.2$  ng/ml is  $\leq 60\%$  is rejected with a target error rate of  $\alpha=0.10$  (actual error 0.095), whereas if the number is 43 or less, then the hypothesis that the percentage achieving PSA level  $\leq 0.2$  ng/ml is  $\geq 75\%$  is rejected with a target error rate of  $\beta=0.10$  (actual  $\beta=0.099$ ). We also will report exact binomial 90% confidence intervals on the observed proportion. Patients that discontinue early or are missing the end of treatment (cycle 6) PSA will be considered failures. Sensitivity analysis on the primary endpoint that includes counting a patient as a success if there is record of PSA level  $\leq 0.20$  ng/ml ever on treatment will be performed. We expect to accrue 2-3 patients per month at the three DF/HCC hospitals, BWH and DFCI and therefore accrual duration is expected to be 24-36 months.

CONFIDENTIAL

This document is confidential. Do not disclose or use except as authorized.

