### **4.2 Registration Process for DF/HCC and DF/PCC Institutions**

The QACT registration staff is accessible on Monday through Friday, from 8:00 AM to 5:00 PM Eastern Standard Time. In emergency situations when a participant must begin

CONFIDENTIAL

This document is confidential. Do not disclose or use except as authorized.

Version 13.0 Protocol Version Date: 1/09/2015

treatment during off-hours or holidays, call the QACT registration line at [contact] and follow the instructions for registering participants after hours.

The registration procedures are as follows:

1. Obtain written informed consent from the participant prior to the performance of any study related procedures or assessments.
2. Complete the protocol-specific eligibility checklist using the eligibility assessment documented in the participant's medical/research record. **To be eligible for registration to the study, the participant must meet each inclusion and exclusion criteria listed on the eligibility checklist.**

**Reminder:** Confirm eligibility for ancillary studies at the same time as eligibility for the treatment study. Registration to both treatment and ancillary studies will not be completed if eligibility requirements are not met for all studies.

3. Fax the eligibility checklist(s) and all pages of the consent form(s) to the QACT at [contact].
4. The QACT Registrar will (a) validate eligibility, (b) register the participant on the study, and (c) enroll the participant when applicable.
5. The QACT Registrar will send an email confirmation of the registration and/or enrollment to the person initiating the registration immediately following the registration and/or enrollment.

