## 13.2 Analysis of Secondary Endpoints

### 13.2.1 Health related quality of life

The primary HRQoL aim is to assess the change from baseline to the end of cycle 6 in the vitality or hormonal function score as well as the sexuality score on the EPIC-26 questionnaire. It is anticipated approximately 75% of patients will have both scores for each domain. A one-sample t-test will be used to assess the overall change in score. To be considered a clinically meaningful difference will be defined as half historical standard deviation for the specific domain. Given 48 evaluable patients, there is 80% power to detect a 0.41 change in the hormonal domain score of the EPIC-26 assuming 2-sided 5% alpha. Results in this study will be evaluated in the context of past research by Sanda et al showing patients that received radiotherapy with non-hormonal therapy had a score on the vitality or hormonal function domain of approximately 80 and a score on the sexuality domain of 26.

Descriptive statistics at each time point and changes over time will be provided for each of the EPIC-26 domains as well as for the PROMIS-Fatigue and PSQ1. Mixed models will be used to explore the impact of time on quality of life adjusting for prognostic baseline factors.

13.2.2 Safety and Tolerability: We will monitor toxicities experienced by all treated patients. Frequency and severity of worst grade 3 or higher treatment-related AEs by type will be reported along with the incidence of overall grade 3 or higher treatment-related AEs. With 71 treated patients, the maximum width of a 90% CI for a given toxicity is 21%. The probability of observing one rare severe toxicity (true rate=5%) is 97%. Tolerability endpoints include the number of dose reductions and treatment interruptions as well as the number of patients that discontinue treatment due to AEs. The safety summary will include clinical laboratory, ECG and vital signs data.

13.2.3 Hormone Levels: Descriptive statistics at each time point and changes over time will be provided for all hormone measures. Paired t-tests and two-sample t-tests (or non-parametric equivalents) will be used to assess significance of change over 6 cycles of treatment in hormone levels for the overall cohort and by status on primary clinical endpoint (yes or no achieving PSA level  $\leq 0.20$  ng/ml at the end of 6 cycles of treatment with enzalutamide and EBRT).

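### Is the primary analysis left without a decision rule if the evaluable number is not exactly 64?

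*Combined protocol and SAP*

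**What the plan says.** Section 13.1 sets the size of the trial: "In a single stage design, seventy-one patients will be enrolled". It then makes an allowance: "Assuming 10% ineligibility, the target evaluable sample size is 64 patients". The hypotheses follow. The null is given as "The null hypothesis is 60% of patients achieving PSA nadir" of 0.2 ng/ml or lower, and the historical 75% is the alternative.

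The decision rule opens with "With a sample size of 64 evaluable patients, if the number achieving PSA level" at or below the threshold: 44 or more rejects a rate of 60% or less (target α 0.10, actual 0.095), and 43 or fewer rejects a rate of 75% or more (target β 0.10, actual 0.099).

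Two further sentences in 13.1 bear on the denominator and the reporting: "Patients that discontinue early or are missing the end of treatment (cycle 6) PSA will be considered failures" and "We also will report exact binomial 90% confidence intervals on the observed proportion".

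Neither 13.1 nor any other section gives a cut-off for a number other than 64.

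**The concern.** The counts 44 and 43 are tied to a number that is only a target. Early discontinuations and missing PSAs stay in as failures, so the evaluable number is 71 minus the ineligible, which need not be 64.

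Two things then look troubling. If 44 were kept at a larger number, the type I error would climb: 0.127 at 65 and 0.417 at 71. And 64 is the smallest number at which one cut-off holds both errors at or below 0.10. At many nearby numbers no cut-off does, so a reader may think that the rule cannot be rebuilt. In a single-arm trial with PSA measured every cycle, the cut-off might then be settled with the success count in view.

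**Working it through.** **Inputs, all from 13.1:** 71 enrolled; 10% ineligible; p0 = 0.60; p1 = 0.75; α and β targets of 0.10; exact binomial error rates.

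**1. The plan's own figures.** With X binomial on n = 64:
- α = P(X ≥ 44 | 0.60) = 0.0953, against 0.095 stated.
- β = P(X ≤ 43 | 0.75) = 0.0993, against 0.099 stated.

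Both reproduce. The projection is 71 × 0.90 = 63.9, about 64.

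**2. How often n is 64.** If each patient is independently ineligible with probability 0.10, the evaluable number N is binomial(71, 0.90). Then P(N = 64) = 0.157, P(N > 64) = 0.426 and P(N < 64) = 0.417.

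**3. Rebuilding the cut-off from the stated null and α.** Take r(n) as the smallest r with P(X ≥ r | n, 0.60) ≤ 0.10, and β(n) = P(X ≤ r − 1 | n, 0.75).

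| n | r | α | β |
|---|---|---|---|
| 60 | 42 | 0.072 | 0.149 |
| 61 | 42 | 0.099 | 0.107 |
| 62 | 43 | 0.083 | 0.122 |
| 63 | 44 | 0.070 | 0.138 |
| 64 | 44 | 0.095 | 0.099 |
| 65 | 45 | 0.080 | 0.114 |
| 66 | 46 | 0.067 | 0.129 |
| 67 | 46 | 0.092 | 0.093 |
| 68 | 47 | 0.078 | 0.106 |
| 69 | 48 | 0.065 | 0.120 |
| 70 | 48 | 0.088 | 0.086 |
| 71 | 49 | 0.075 | 0.099 |

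There is one answer at every n, and it returns the plan's 44 at n = 64. Only β drifts above 0.10, at 60–63, 65, 66, 68 and 69. Those eight numbers have total probability 0.706 under step 2; numbers below 60 add 0.048.

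**4. What the competing convention would change.** Holding β ≤ 0.10 instead gives the largest cut-off c with P(X ≤ c − 1 | n, 0.75) ≤ 0.10. From 60 to 71 these are 41, 41, 42, 43, 44, 44, 45, 46, 46, 47, 48, 49: equal to r at 64, 67, 70 and 71, and one lower at the other eight. The chance that the two conventions disagree is

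D(p) = Σ P(N = n) × P(c(n) ≤ X < r(n) | n, p), summed over all attained n.

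At 10% ineligible, D is 3.5% at p = 0.60, peaks at 8.2% near p = 0.68, and falls to 3.7% at p = 0.75. Putting 0.95 or 0.85 in place of 0.90 in P(N = n), as assumed alternatives, gives 2.7% to 6.7% and 5.3% to 11.7%.

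**5. Whether the 90% interval is a rival rule.** At 44 of 64 the exact lower limit is 0.579, below 0.60, although the count rule rejects. The first count whose lower limit exceeds 0.60 is 46 (0.612). The interval has 5% in each tail, so it describes the estimate and does not replace the test.

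**The case for a change.** The best case for a change is that 13.1 states a two-way decision with equal error targets and does not say which target yields when both cannot be met. At 45 of 66 the one-sided p-values are 0.108 against 60% and 0.129 against 75%; at 47 of 69 they are 0.104 and 0.120. Neither hypothesis is rejected at 0.10, an outcome that the wording does not foresee. One sentence in the plan would remove the question at no cost in patients.

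The arithmetic stands, and so does the silence. But the two targets do not have equal standing once the data are in. Section 13.1 names 60% as the null, and rejecting it is the positive finding, so α guards the claim. β was used to choose the size of the trial, and a slightly different power at the attained number is routine. At 45 of 66 the report says that 60% was not rejected and gives the estimate and interval.

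The alarming α values for a carried-over 44 do not stand. The text ties 44 to 64 patients, so using it elsewhere would depart from the plan.

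Nor is there much room to steer the denominator. Missing PSAs and discontinuations remain in it as failures, and eligibility is checked centrally under Section 4.2 ("The QACT Registrar will (a) validate eligibility, (b) register the participant on the study, and (c) enroll the participant when applicable"), with registration required before treatment under Section 4.1. If nearly everyone is eligible, n is 70 or 71, where one cut-off meets both targets.

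Finally, Sections 1.1 and 2.3 do not make a phase III trial depend on this count. Section 1.1 calls the study exploratory and sets estimation of a proportion as the objective, which the exact interval serves at any n.

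**Conclusion.** No change is called for. The plan omits how the count rule carries over to an attained number other than 64, but its stated null, direction, α and exact method already determine the cut-off, and at 64 its figures are correct. The word evaluable, though undefined, can be read from the ineligibility allowance together with the rule that missing results are failures.

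The remaining ambiguity is whether an analyst might hold β instead of α. That is one count at eight of the twelve numbers from 60 to 71, and a different conclusion in about 3.5% to 8.2% of trials. That range assumes 10% independent ineligibility and true rates of 60% to 75%; it moves to 2.7% to 6.7% at 5% ineligible and 5.3% to 11.7% at 15%. The cost of the natural reading is β of 0.106 to 0.149 at those eight numbers, a modest loss of power from discreteness that does not weaken a rejection of the null.
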